12. REGULATORY ISSUES

12.1. ETHICS APPROVAL

The Study Coordination Centre has obtained approval from the Queen Square Research Ethics Committee (REC) and Health Regulator Authority (HRA). The study must also receive confirmation of capacity and capability from each participating NHS Trust before accepting participants into the study or any research activity is carried out. The study will be conducted in accordance with the recommendations for physicians involved in research on human subjects adopted by the 18th World Medical Assembly, Helsinki 1964 and later revisions.

12.2. CONSENT

The Informed Consent form will be electronic and submitted through the Qualtrics® platform (offered by Imperial College London). After submission by the parent/carer, an automatic email will be sent to his/her email containing a link to access and save their true copy of the informed consent form. All will be performed in line with guidance from the HRA and MHRA, taken by a member of the research team who has been delegated the duty by the PI as recorded on the Sponsor's Delegation of Responsibilities Log and recorded in writing which will be sent to the researcher via email. No hard copies will be retained. Those confirming informed consent will have had formal training in informed consent and completed GCP training. Consent to enter this study will be obtained after a full account has been provided of its nature, purpose, risks, burdens and potential benefits, and the patient has had the opportunity to deliberate. The patient will be allowed to specify the time they wish to spend deliberating. Patients are encouraged to consider taking part, and discuss the study with their physician, family, friends and whoever else they wish before deciding. The PI or designee will explain to the parents that their child is under no obligation to enter the study and they can withdraw at any time during the study, without having to give a reason. Participant's parent/carer will be given a copy of the most recent approved PIS

as well. The electronic consent form will be retained at the study site [one filed in the medical notes, and one filed in the Study Master File (SMF)].

12.3. CONFIDENTIALITY

The Chief Investigator will preserve the confidentiality of participants taking part in the study and is registered under the Data Protection Act. Data will be anonymised.

12.4. INDEMNITY

Imperial College London holds negligent harm and non-negligent harm insurance policies which apply to this study.

12.5. SPONSOR

Imperial College London will act as the main Sponsor for this study. Delegated responsibilities will be assigned to the NHS trusts taking part in this study.

12.6. FUNDING

Asthma UK Centre for Applied Research (AUKCAR) is funding this study.

12.7. AUDITS

The study may be subject to audit by Imperial College London under their remit as sponsor and other regulatory bodies to ensure adherence to GCP and the UK Policy Framework for Health and Social Care Research.

13. DATA MANAGEMENT AND QUALITY ASSURANCE

13.1. CONFIDENTIALITY

All data will be handled in accordance with the General Data Protection Regulation (GDPR) (2018), NHS Caldecott Principles, The UK Policy Framework for Health and Social Care Research, and the condition of the REC approval. The Case Report Forms (CRFs) will not bear the child participants' name or other personal identifiable data. Identification will be performed through the participants' Identification Number (ID). No data will be shared with any external organisation without appropriate consent and data sharing agreement in place, as applicable.

13.2. DATA COLLECTION TOOL

Case Report Forms (CRF) will be designed by the trial coordinator and PI, and the final version will be reviewed and discussed with the study Sponsor. Researchers will complete electronic versions of the CRF to reduce errors compared to transcribing from paper to an electronic database. It is the Investigator's responsibility to ensure the accuracy of all data entered and recorded in the CRFs. The Delegation of Responsibilities Log will identify all study personnel responsible for data collection, entry, handling and managing the database.

13.3. DATA HANDLING AND ANALYSIS

The Informed Consent form will be electronic and submitted through the Qualtrics® platform (offered by Imperial College London). After submission by the parent/carer, an automatic email will be sent to his/her email containing a link to access their true copy of the informed consent form. All data will be stored in the Imperial College London Microsoft Office 365 cloud account of [name], and all will be done in accordance with the Imperial College London's data policy. Data will be backed up in a second Imperial College London Microsoft Office 365 cloud account of [name] and in accordance with the aforementioned policy. The CI will act as the Data Custodian for the study. [name] (study coordinator) will be responsible for data entry and quality. He will also be responsible for data analysis, with support from the study statistician. Data analysis will be performed on separate occasions to data entry.

13.4. ARCHIVING ARRANGEMENTS

Data will be kept in a secure storage unit at the Sponsor site for 10 years. The study documents (including the Study Master File (SMF), Case Report Forms (CRFs), Informed Consent Forms along with the study database) will be kept for 10 years. The study database will be kept electronically on Imperial College London's computer network, in a password-protected encrypted folder. The PI is responsible for the secure archiving of study documents. The approved repository for longer retention of local materials for studies that involve Imperial College London patients is Box-It Storage UK. The study documentation will be prepared for archiving by the research team in line with the Research Office Archiving SOP and the transfer will be arranged by the Research Office. After 10 years all data, including audio and video recordings, will be destroyed in accordance with Imperial College London's data policy.

13.5. DIRECT ACCESS TO SOURCE DATA

The Investigator(s)/institution will permit study-related monitoring, audits, REC review, and regulatory inspection(s), providing direct access to source data/documents. Parents will be informed of this during the informed consent discussion. Parents will be asked to consent to provide access to their medical notes.

14. INSURANCE AND INDEMNITY

NHS bodies are liable for clinical negligence and other negligent harm to individuals covered by their duty of care. NHS Institutions employing researchers are liable for negligent harm caused by the design of studies they initiate. The provision of such indemnity for negligent harm will be stated to the parent/carer of the child participant.

15. STUDY MANAGEMENT

The day-to-day management of the study will be co-ordinated by [name].

16. PUBLICATION POLICY

Data ownership rights will lie with the institution.

17. STATEMENT OF COMPLIANCE

The study will be conducted in compliance with the protocol, Sponsor's Standard Operating Procedures (SOPs), GCP and the applicable regulatory requirement(s).

The study conduct shall comply with all relevant laws of the EU if directly applicable or of direct effect and all relevant laws and statutes of the UK country in which the study site is located including but not limited to, the Human Rights Act 1998, the General Data Protection Regulation (GDPR) (2018), the Medicines Act 1968, and with all relevant guidance relating to medicines and clinical studies from time to time in force including, but not limited to, the ICH GCP, the World Medical Association Declaration of Helsinki entitled 'Ethical Principles for Medical Research Involving Human Subjects' (2008 Version), the NHS Research Governance Framework for Health and Social Care (Version 2, April 2005).

This study will be conducted in compliance with the protocol approved by HRA and according to RGF standards. No deviation from the protocol will be implemented without the prior review and approval of the Sponsor and HRA except where it may be necessary to eliminate an immediate hazard to a research subject. In such case, the deviation will be reported to the Sponsor and the REC as soon as possible.

19. APPENDICES

19.1. APPENDIX 1: RECRUITMENT PLAN

The recruitment period will approximately last 9 months, and all preschool wheezers can join the study at any point. Parents/Carers of preschool children presenting to primary care or to the Emergency Department (ED) or to secondary care (e.g., outpatients) as well as those identified from primary care records and who have been diagnosed by a GP or paediatrician with wheezing, will be approached by collaborating doctors and nurses who will ask their parents if they are willing to have their child participate in the study. The list of recruitment sites is given below (Table 1). A patient information sheet will be given, containing all the information regarding the project and the contact details of the research team, for further questions. They will be asked for their willingness to give the study team permission to contact them and discuss recruitment, and if so, they will submit their contact details in an electronic form made with the Qualtrics® questionnaire platform (offered by Imperial College London), which allows gathering data according to the GCP guidelines and as used for years in the Breathing Together study (19). Additionally, the questionnaire form submission will not collect parents' IP address or geolocation. This form will be available online in the Asthma UK Centre for Applied Research's (AUKCAR) website. The initial introduction will be made either by the clinical team (above) with the study team contacting them later to give more information or by [name] if he is there in person.

Name of Participating NHS Organisation	University of Oxford NHS Hospitals
Location	Activity
Oxford University Hospitals NHS Foundation Trust	Participant Identification, Review Visits, Biomarker testing (finger prick test, skin prick test, collection of FeNO in a bag) Participant Identification
John Radcliffe Hospital	
Oxfordshire Clinical Commissioning Group	
Bicester Health Centre	
White Horse Medical Practice	
Oxfordshire BCSC (Horton Hospital)	
Whitchurch Surgery	
Norden House Surgery	
The Swan Practice	
Windrush Surgery	
CRN East Midlands	

Table 1. Patient identification and recruitment sites

Study procedures	Eligibility assessment	Before starting the study
Child participant identification	X	
Contact information submission	X	
Telephone/email contact with parents	X	
Inclusion/Exclusion criteria		X
Patient Information Sheet		X
Face-to-face project discussion		X
Electronic Informed Consent		X

19.2. APPENDIX 2: FOLLOW-UP PLAN

We will arrange for a short monthly electronic questionnaire to be sent by email to the parents/carers, in order to record on a monthly basis, the days their child was out of childcare, days the carer missed from work, unscheduled health care visits and use of rescue therapy or oral corticosteroids (including dosage) (Appendix 4: Monthly Questionnaire). In addition, we will record the children's TRACK™ score (Test for Respiratory and Asthma Control in Kids) (Appendix 3: TRACK™ score questionnaire) every 3 months, to assess wheeze control. The questionnaires will be made and sent through the Qualtrics® questionnaire platform (offered by Imperial College London), which allows data gathering data according to the GCP guidelines and as used for years in the Breathing Together study (19). Additionally, the questionnaire form submission will not collect parents' IP address or geolocation. There will also be review visits every 3 months, to evaluate their progression in person, but if not feasible, video calls will be arranged through Microsoft Teams.

	Months											
	1	2	3	4	5	6	7	8	9	10	11	12
Primary Care Visit		X			X			X				X
Video Call (Microsoft Teams) ¹		X			X			X				X
Biomarker Testing ²			X ³									
TRACK™ Score Questionnaire ⁴			X			X			X			X
Monthly Questionnaire	X	X	X	X	X	X	X	X	X	X	X	X
Focus Group												X

Table 2. The follow-up plan after preschool wheezers' recruitment.

¹ In case they are not available for primary care visit

² Testing the 3 biomarkers, blood eosinophils, atopic sensitisation and FeNO (offline method).

³ A second testing will be performed 3 months after the first one and will be **optional**. Parents will be informed through the patient information sheet, as well as in person that they have the option to deny participation of their child in this second testing. It is written in the informed consent form as well.

⁴ The TRACK™ score will be sent to the parents/carers by email or SMS every 3 months and will be incorporated to the monthly questionnaire. They will be sent through the Qualtrics® questionnaire platform.

19.3. APPENDIX 3: TRACK™ SCORE QUESTIONNAIRE (TEST FOR RESPIRATORY AND ASTHMA CONTROL IN KIDS)

1. During the past 4 weeks, how often was your child bothered by breathing problems, such as wheezing, coughing or shortness of breath?
					
Not at all	Once or twice	Once every week	2 or 3 times a week	4 or more times a week	
 20	 15	 10	 5	 0	

2. During the past 4 weeks, how often did your child's breathing problems (wheezing, coughing, shortness of breath) wake him or her up at night?
					
Not at all	Once or twice	Once every week	2 or 3 times a week	4 or more times a week	
 20	 15	 10	 5	 0	

3. During the past 4 weeks, to what extend did your child's breathing problems, such as wheezing, coughing or shortness of breath, interfere with his or her ability to play, go to school or engage in usual activities that a child should be doing at his or her age?
					
Not at all	Slightly	Moderately	Quite a lot	Extremely	
 20	 15	 10	 5	 0	

4. During the past 3 months, how often did your need to treat your child's breathing problems (wheezing, coughing or shortness of breath) with quick relief medications (e.g., albuterol, Ventolin®)
					
Not at all	Once or twice	Once every week	2 or 3 times a week	4 or more times a week	
 20	 15	 10	 5	 0	

5. During the past 12 months, how often did you child need to take oral corticosteroids (e.g., prednisone, prednisolone, Decadron®)
					
Not at all	Slightly	Moderately	Quite a lot	Extremely	
 20	 15	 10	 5	 0	

Total Score

Figure 1. The TRACK™ Score Questionnaire. TRACK (Test for Respiratory and Asthma Control in Kids) is a trademark of AstraZeneca group of companies © 2009. TRACK score less than 80 means that the child's breathing problems are out of control. TRACK score above 80 means that the child's breathing problems seem to be in control.

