DESIGN:	This is a pragmatic, observational study in children with pre-school wheeze. After recruitment and at the first study visit, biomarkers (allergic sensitisation, exhaled nitric oxide and peripheral blood eosinophil count) will be measured. The children will be followed for a year, with monthly electronic questionnaires and study visits every 3 months. All treatment and routine monitoring decisions will be at the discretion of the children's general practitioner (GP) or paediatrician (as per usual clinical practice), blinded to the study measurements. There will be a second optional biomarker measurement 3 months after the first one, in their second study visit. Parents/Carers of preschool children presenting either to primary care or to the Emergency Department (ED) or to secondary care (e.g., outpatients) as well as of those identified from primary care records and have been diagnosed by their GP or paediatrician with wheezing, will be identified by collaborating doctors and nurses who will ask the parents if they are willing to have their child participate in the study (the list of recruitment sites is given in Appendix 1 – Recruitment Plan). A patient information sheet will be given, containing all the information regarding the

[figure not shown]

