5. STUDY'S AIM AND OBJECTIVES

AIM: To obtain pilot data to test the hypothesis that aeroallergen sensitisation (confirmed by a wheal formation with a diameter ≥ 3 mm after a skin prick test is performed), FeNO (offline method) ≥ 10 ppb and a peripheral blood eosinophil count $\geq 300/\mu\text{l}$, alone or in combination, can predict future wheezing exacerbations in preschool children as well as response to treatment with inhaled corticosteroids, as a preliminary to a large, randomised controlled trial. Also, that these tests are acceptable to families.

OBJECTIVES:

- To recruit 100 preschool children with a history of wheeze, aged one to five years old, and determine atopic status, peripheral blood eosinophil count (point of care test) and FeNO (offline method).
- To evaluate the feasibility and acceptability of these tests
- To categorize the children according to the biomarkers tested and assess whether any or all, alone or in combination, predict future wheezing exacerbations as well as determine the clinical outcome over one year
- To obtain parents' and doctors' insights into whether the biomarkers mentioned above could be used in a future intervention study.

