Follow-up: We will arrange for a short monthly electronic questionnaire to be sent by email to the parents/carers, in order to record on a monthly basis, the days their child was out of childcare, days the carer missed from work, unscheduled health care visits and use of rescue therapy or oral corticosteroids (including dosage) (Appendix 4: Monthly Questionnaire). In addition, we will record the children's TRACK™ score (Test for Respiratory and Asthma Control in Kids) (Appendix 3: TRACK™ score questionnaire) every 3 months, to assess wheeze control. The questionnaires will be made and sent through the Qualtrics® questionnaire platform (offered by Imperial College London). There will be review visits every 3 months, to evaluate their progression in person, but if not feasible, video calls will be arranged through Microsoft Teams. Correct use of spacers will be ensured after guiding parents on how to use them and will be done by their GP or paediatrician as well as from [name] who is a registered pharmacist in the UK.

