6.1. STUDY OUTCOME MEASURES

Primary outcome:

Acute attacks of wheeze defined as requiring an unscheduled health care visit

Secondary outcomes:

- Carer days off work
- Days the child unable to attend childcare facility
- Use of oral corticosteroids
- Use of inhaled β -2 agonist (rescue therapy)
- Assessment if children's respiratory or wheezing condition is under control by using the TRACK™ score questionnaire (Test for Respiratory and Asthma Control in Kids) (Appendix 3).

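### No TRACK score is scheduled at entry (the first is at month 3), so later wheeze control cannot be compared with, or adjusted for, control at entry.

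*Combined protocol and SAP*

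**What the plan says.** Section 6.1 lists TRACK as a secondary outcome: "Assessment if children's respiratory or wheezing condition is under control by using the TRACK™ score questionnaire". Section 6 has it recorded "every 3 months, to assess wheeze control", and the study summary, section 7.1, section 9 and Appendix 2 give the same interval. Footnote 4 of Table 2 in Appendix 2 sets out the delivery: "The TRACK™ score will be sent to the parents/carers by email or SMS every 3 months and will be incorporated to the monthly questionnaire". In that table the row "TRACK™ Score Questionnaire ⁴" is marked at months 3, 6, 9 and 12, and the columns begin at month 1.

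The entry procedures are described elsewhere. For the first study visit the study summary says "biomarkers (allergic sensitisation, exhaled nitric oxide and peripheral blood eosinophil count) will be measured". Sections 6 and 7.1 add the video questionnaire, shown to the parent after consent. The pre-study table in Appendix 1 runs from identification to consent. None of these mentions TRACK.

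The aim in section 5 is for the biomarkers to predict exacerbations "as well as response to treatment with inhaled corticosteroids".

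**The concern.** Response to a treatment is naturally read as better control than before. Section 4.3 itself describes good ICS response in an earlier crossover study partly as improved control of chronic symptoms. TRACK is the listed measure of control here, yet it has no starting value.

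This matters more than it would in a randomised trial. The treating clinician chooses the treatment, and children come from the emergency department, outpatients, primary care consultations and primary care records. Severity at entry is therefore likely to vary, and nothing in the design balances it between biomarker groups. If the groups differ on TRACK at month 3 or later, the data cannot show whether the gap arose during follow-up or was there at the start. A pilot meant to inform power calculations would also give no entry mean, entry SD or entry-to-follow-up correlation for TRACK.

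**Working it through.** The plan gives no power or precision figure for TRACK, so there is none to reproduce. The check has four parts.

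**1. Scores available (Table 2).**
- Scores per child: 4 (months 3, 6, 9, 12). At or before entry: 0.
- Within-child changes available: 4 × 3 / 2 = 6 pairs. The longest span is 12 − 3 = 9 months.
- With an entry score: 5 scores, 5 × 4 / 2 = 10 pairs, longest span 12 months.

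**2. Can month 3 stand in for entry?** The recall periods are in Appendix 3, and each item carries up to 20 points. Taking entry as month 0, the month-3 score covers:

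| Item | Recall | Period covered | Points |
|---|---|---|---|
| 1 to 3 | 4 weeks | about months 2 to 3 | 60 |
| 4 | 3 months | months 0 to 3 | 20 |
| 5 | 12 months | months −9 to 3 | 20 |

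So 60 + 20 = 80 of 100 points describe only time after entry. Item 5 alone reaches back before it. Month 3 is a follow-up score.

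**3. Could an entry gap pass for a follow-up gap?** Let r be the correlation between entry and follow-up TRACK within a biomarker group, with equal SDs at the two times and a linear relation. Suppose the groups differ by δ SD at entry and the biomarker has no further association with the later score. The expected follow-up gap is then r × δ. For each 1 SD of entry difference, r = 0.3, 0.5 or 0.7 carries 0.3, 0.5 or 0.7 SD forward. The documents give neither r nor δ, so this shows the mechanism and does not estimate a bias.

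**4. Precision gained by adjustment (r assumed).** Residual variance is 1 − r². The detectable standardised difference at two-sided 5% and 80% power is

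(1.960 + 0.842) × √(1/n₁ + 1/n₂) × √(1 − r²).

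N = 100 is from section 5 and the 5% level from section 11. Two-sidedness, power, the group splits and r are assumptions, and no dropout is allowed for.

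| r | Residual variance | Cut | Detectable, 50:50 | Detectable, 30:70 |
|---|---|---|---|---|
| none | 1.00 | – | 0.560 SD | 0.611 SD |
| 0.3 | 0.91 | 9% | 0.535 SD | 0.583 SD |
| 0.5 | 0.75 | 25% | 0.485 SD | 0.529 SD |
| 0.7 | 0.51 | 49% | 0.400 SD | 0.437 SD |

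**The case against.** Several points on the other side stand, and they limit what can be claimed.

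- **Change over time.** A reader might infer that change in wheeze control cannot be measured for any child. That is not so: any child with two completed scores gives a within-child change between months 3 and 12. Only change from entry is lost.
- **The listed outcome.** Section 6.1 defines it as whether the condition is under control, and Appendix 3 supplies a cut-off of 80. No change-from-baseline endpoint is stated, so the outcome can be reported as defined.
- **"Pre-treatment".** A reader might call the missing value a pre-treatment score. Inclusion requires that the clinician has already decided to prescribe. Children found from records may have been treated for some time, and the biomarker visit is booked for a stable period after consent. An entry score is therefore not a pre-treatment score for every child. Nor can one say that every planned score follows three months of treatment, since timing rests with the clinician and a child may receive no ICS.
- **Entry severity.** Nothing in the documents shows that later TRACK mostly reflects it, or that biomarker-positive children start worse. At the assumed correlations the entry score explains less than half of the later variance.
- **Other evidence on ICS response.** The plan also records why ICS was stopped, added medication and referral, and has monthly data on wheeze and medication. These help, but the month-1 questionnaire already covers time after entry and uses a different scale.
- **Silence of Table 2.** It is titled "Table 2. The follow-up plan after preschool wheezers' recruitment", and its biomarker mark is for the repeat test ("A second testing will be performed 3 months after the first one and will be optional"). It omits the entry biomarker test as well, so a missing entry mark for TRACK proves little by itself. The point rests on the separate entry descriptions being silent too.
- **Unseen material.** The section 3 flowchart, and the Table 3 of Appendix 1 cited in sections 6 and 7.1, could not be checked.

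**Conclusion.** The point holds in limited form. In the text that could be read, no child has a TRACK score scheduled at entry. Change from entry, and adjustment for control at entry, are therefore unavailable, while control status at four times and change over up to 9 months remain.

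The loss falls on interpretation: a group difference at follow-up could be an entry difference carried forward. With assumed correlations of 0.3 to 0.7, adjustment would also remove 9% to 49% of residual variance.

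This concerns one secondary outcome in a feasibility study, and the remedy is cheap. Confidence is medium: if the flowchart or the unseen part of Appendix 1 does schedule an entry TRACK, what remains is to state it in the entry-visit text and to plan its use in the analysis.

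**What to change.** 1. Add a month-0 column to Table 2, and have the parent complete TRACK at the first biomarker visit before any test is done. The eosinophil count is ready in about 2 minutes and families are told the skin prick results, so the order matters. Call it an entry score, and record treatment in use on that day.
2. Add to section 11 a comparison of follow-up TRACK between biomarker groups adjusted for the entry score. That section now names only unadjusted tests, so check that the chosen software can fit the model.
3. Compare groups with each other, and do not read change against zero. Scores taken soon after an attack tend to rise anyway, and section 4.3 reports spontaneous improvement in 60 of 300 children (20%) in the earlier crossover study.
4. Note that item 5 recalls 12 months. At month 3 its window shares 9 of 12 months with the entry window, and the two are distinct only at month 12.

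If no entry score is added, state that TRACK describes control status during follow-up only and will not be used to judge ICS response.

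The cost is a few minutes of parent time at an existing visit, using an existing form, and one adjusted analysis. An entry score does not remove confounding by severity that TRACK misses, or by the clinician's choice of treatment.

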11. STATISTICS AND DATA ANALYSIS

The statistical analysis of the project will be done by [name] in collaboration with [name] (University of Edinburgh) and the Asthma UK Centre for Applied Research (AUKCAR), the funder of the study. Statistical analyses will use the GraphPad PRISM software package. A normality test will be performed to assess normal (Gaussian) distribution (e.g., the Shapiro-Wilk test. If there is normal distribution, then parametric tests will be used, otherwise non-parametric tests. Level of significance is set as a p value <0.05. The tests that are currently planned to be used are:

- **Chi-Squared test (x²-test)**

This test allows assessing if a variable is similar between two or more groups or to test if two or more variables are related/dependent

- **Fisher's Exact test**

This test is used when chi-squared values are <5, usually with a small sample size.

- **Student t-test or Mann-Whitney test**

These tests are used for comparison between two study groups. The first is for normally distributed quantitative variables and the second for non-normally distributed quantitative variables.

Data and all appropriate documentation will be stored for a minimum of 10 years after the completion of the study, including the follow-up period.

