19.4. APPENDIX 4: MONTHLY QUESTIONNAIRE

Introduction: Please take a moment to complete the following questionnaire relating to your child's wheezing condition. The questions will help us identify wheezing exacerbations and assess your child's quality of life.

Question 1: Did your child experience any wheezing symptoms during the last month?

Not at all	Once or twice	Once every week	2 or 3 times a week	4 or more times a week
				

Question 2: Was the child unable to go to childcare because of breathing problems?

Yes	No	N/A
		

If **yes**, please state how many days: _____ (Number)

Question 3: Did you have to take your child for an emergency appointment with your GP, urgent care or hospital because of wheezing?

Not at all	Once or twice	Once every week	2 or 3 times a week	4 or more times a week
				

Question 4: Was your child treated with inhaled or oral corticosteroids?

Yes	No
	

If **yes**, what was the dose, frequency and duration?

Dose:	Frequency:	Duration:
_____	_____	_____

Question 5: Was your child given β 2 agonists (blue inhaler, rescue therapy)?

Yes	No
	

If **yes**, what was the dose, frequency and duration?

Dose:	Frequency:	Duration:
_____	_____	_____

Question 6: Did you have to take days off work because your child had wheezing or breathing difficulties?

Yes	No
	

If **yes**, how many days did you take? Specify number: _____ (days)

Survey's ending message: "We thank you for your time spent taking this survey. Your response has been recorded."

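### TRACK form in Appendix 3: item 5 asks for a frequency but offers degree words, and a total of exactly 80 has no control class

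*Combined protocol and SAP*

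**What the plan says.** Section 6.1 lists, among the secondary outcomes, whether the child's condition is under control as judged by TRACK. Appendix 3 (section 19.3) prints the form: five items, each scored 20, 15, 10, 5 or 0.

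- **Item 5** asks "During the past 12 months, how often did you child need to take oral corticosteroids". Its printed answers are *Not at all* (20), *Slightly* (15), *Moderately* (10), *Quite a lot* (5) and *Extremely* (0).
- **The caption** gives two rules: "TRACK score less than 80 means that the child's breathing problems are out of control" and "TRACK score above 80 means that the child's breathing problems seem to be in control".
- **Timing.** The notes to Table 2 in Appendix 2 state: "The TRACK™ score will be sent to the parents/carers by email or SMS every 3 months". The table places TRACK at months 3, 6, 9 and 12.
- **Analysis.** Section 11 introduces its methods with "The tests that are currently planned to be used are" and then lists chi-squared, Fisher, t and Mann-Whitney tests. It gives no TRACK scoring rule or cut-off and does not say whether TRACK is analysed as a class or as a number.

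Steroid use is also collected monthly. Section 6 describes recording "use of rescue therapy or oral corticosteroids (including dosage"), and Question 4 in Appendix 4 asks "Was your child treated with inhaled or oral corticosteroids", followed, if yes, by "what was the dose, frequency and duration".

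**The concern.** Items 1, 2 and 4 also ask *how often*, and they carry frequency answers. Item 3 asks about extent, and its degree answers fit. Item 5 pairs a frequency question with item 3's row. A parent whose child had one or two courses has no stated basis for choosing between the four words below *Not at all*, and the choice moves the total by up to 15 points.

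The caption fault is independent of this. It leaves one attainable total without a class, including for children whose item 5 answer is perfectly clear.

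At stake is a declared secondary outcome, collected up to four times in each of 100 children (4 × 100 = 400 questionnaires). The study is also meant to supply pilot data for a later randomised trial, so an uncorrected form could be carried forward.

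**Working it through.** **Inputs** (all from Appendix 3): five items scored 0, 5, 10, 15 or 20; below 80 is out of control; above 80 is in control. The plan gives no derived figure to reproduce here.

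**Step 1: is 80 attainable?** Totals run from 0 to 100 in steps of 5, so yes; for example 15 + 15 + 15 + 15 + 20 = 80. Of the 5⁵ = 3125 answer patterns, 2999 total less than 80, 56 more than 80 and 70 exactly 80 (2999 + 56 + 70 = 3125). The 70 have no class. These are counts of patterns, not expected frequencies.

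**Step 2: who can land on 80?** Let T be the total of items 1 to 4, so T = 0, 5, …, 80 (17 values).

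- No course (item 5 = 20): T + 20 = 80 only when T = 60.
- At least one course (item 5 = 15, 10, 5 or 0): 80 is reached at T = 65, 70, 75 or 80 respectively.

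**Step 3: when does the item 5 word alone decide the class?** For a child with at least one course, the total is T plus 15, 10, 5 or 0:

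| T | Totals (item 5 = 15 / 10 / 5 / 0) | Class if 80 is in control | Class if 80 is out of control |
|---|---|---|---|
| 60 | 75 / 70 / 65 / 60 | all out | all out |
| 65 | 80 / 75 / 70 / 65 | in / out / out / out | all out |
| 70 | 85 / 80 / 75 / 70 | in / in / out / out | in / out / out / out |
| 75 | 90 / 85 / 80 / 75 | in / in / in / out | in / in / out / out |
| 80 | 95 / 90 / 85 / 80 | all in | in / in / in / out |

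Below T = 60 every word gives out of control. The class therefore varies at T = 65, 70, 75 if 80 is in control, or at T = 70, 75, 80 if it is out of control. Either way this is 3 of 17 totals.

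**Step 4: does anything else in the documents repair this?** No. The study summary and section 6.1 name the outcome without a cut-off, and section 11 is silent. Nothing assigns 80 or gives other answers for item 5.

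**The case against.** **The appendix may not be the form in use.** Questionnaires go out through Qualtrics, and the live version is not shown. A copying slip confined to the appendix is quite possible. This stands, and it makes checking the live form the first step.

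**TRACK may be analysed as a number.** Section 11 allows for numerical comparisons, and the gap at 80 would then have no effect. This stands too, although the wording of the outcome in section 6.1 favours a class. The item 5 fault remains under either analysis.

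**The reach is small.** This is one of five secondary outcomes in a feasibility study. Oral corticosteroid use is a separate outcome collected monthly, so that information does not depend on item 5. This is fair.

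Three stronger readings are tempting, and the documents do not support them:

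- A reader might infer that both faults leave classes undefined. Only the gap at 80 does. Every item 5 answer has a printed score, so that fault makes the score unreliable, and the class too near the cut-off.
- A reader might take 3 of 17, or 70 of 3125, as the share of children affected. The documents give no score distribution, so that share cannot be computed.
- A reader might expect twelve monthly answers of *No* to Question 4 to rule out a course at month 12. Question 4 combines inhaled and oral steroids and prints no recall window (only Question 1 refers to the last month). All twelve forms would also have to be returned. It can serve only as a consistency check.

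**Conclusion.** Both faults are present in the printed text. The item 5 labels are complete and each has its own score, and the caption is plain prose, so a PDF-reading error is unlikely.

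If the form is used as printed, item 5 gives an unreliable score, spanning 15 points, for children with at least one course. Near the cut-off the chosen word can decide the class. Any child totalling exactly 80 has no class until one is assigned. The first consequence assumes that the live form copies Appendix 3; the second assumes that TRACK is analysed as a class. Only the TRACK secondary outcome is affected. The correction should be made because it is cheap and the outcome is declared, but the finding does not threaten the study's main conclusions.

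**What to change.** 1. Check the live form and Appendix 3 against the licensed instrument, and use that instrument's item 5 answers. They cannot be inferred from the documents: the weekly categories of items 1, 2 and 4 do not obviously suit steroid use over 12 months.
2. State in Appendix 3 and section 11 which class includes exactly 80, following the instrument's scoring guide.
3. If scores were already collected with the printed words, flag those where item 5 is not *Not at all* and items 1 to 4 total 65 to 75 (if 80 is in control) or 70 to 80 (if it is out of control). Report the class over item 5 = 15, 10, 5 and 0. Label this a worst-case bound, because it ignores the order of the words ticked.
4. At month 12, compare item 5 with the monthly Question 4 entries where these identify oral courses, as a consistency check only.

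**Cost:** one answer row, one cut-off line and one sentence in section 11. An amendment may be needed, since section 17 bars deviations without prior approval from the Sponsor and HRA. Scores taken before and after the correction will not be fully comparable.
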